8.3.5	Baseline Descriptive Statistics.....	Error! Bookmark not defined.
9	SUPPORTING DOCUMENTATION AND OPERATIONAL CONSIDERATIONS.....	9
9.1	Regulatory, Ethical, and Study Oversight Considerations.....	9
9.1.1	Informed Consent Process	9
9.1.2	Study Discontinuation and Closure	9
9.1.3	Confidentiality and Privacy	10
9.1.4	Quality Assurance and Quality Control	10
9.1.5	Data Handling and Record Keeping.....	10
9.1.6	Protocol Deviations.....	11
9.1.7	Conflict of Interest Policy.....	11
9.2	Abbreviations.....	12
10	REFERENCES	13

STATEMENT OF COMPLIANCE

The trial will be conducted in accordance with International Conference on Harmonisation Good Clinical Practice (ICH GCP) and applicable United States (US) Code of Federal Regulations (CFR). The Principal Investigator will assure that no deviation from, or changes to, the protocol will take place without prior documented approval from the Institutional Review Board (IRB), except where necessary to eliminate an immediate hazard(s) to the trial subjects. All personnel involved in the conduct of this study have completed Human Subjects Protection and ICH GCP Training.

The protocol, informed consent form(s), recruitment materials, and all subject materials will be submitted to the local Institutional Review Board (IRB) for review and approval. Approval of both the protocol and the consent form must be obtained before any subject is enrolled. Any amendment to the protocol will require review and approval by the IRB before the changes are implemented to the study. All changes to the consent form will be IRB approved; a determination will be made regarding whether a new consent needs to be obtained from subjects who provided consent, using a previously approved consent form.

1 PROTOCOL SUMMARY

1.1 SYNOPSIS

Title:	Non-Surgical Treatment for Rotator-Cuff Tears using Platelet-Rich-Plasma
Study Description:	The purpose of the study was to compare the effects of an injection of "Platelet-Rich Plasma" (PRP) versus a combination of steroid/anesthetic in patients with partial tears of the supraspinatus muscle. Platelet rich plasma is a concentration of blood cells called platelets in a suspension of the liquid plasma portion of blood.
Objectives:	To identify the utility of Platelet-Rich Plasma (PRP) in the treatment of partial thickness tears of the rotator cuff.
Endpoints:	Six-month observation period.
Study Population:	Males and females age 18 - 65 years old.
Phase:	1
Description of Study Intervention:	
 • Treatment arm: PRP injection via ultrasound guidance • Control arm: Corticosteroid + anesthetic agent via ultrasound guidance
Study Duration:	July 2014 – March 2021
Subject Duration:	Six months

1.2 SCHEDULE OF ACTIVITIES (SOA)

2 INTRODUCTION

2.1 STUDY RATIONALE

This research study will test a medical procedure's ability to assist in the healing process of Partial-Thickness Rotator Cuff Tears (PTRCT). The procedure uses an isolation of growth factors and platelets called "Platelet-Rich Plasma" (PRP) isolated from your own blood and re-injected to the site of damage, under ultrasound guidance. This procedure is currently being done across the United States and worldwide and has been demonstrated as a safe procedure. Limited research on this procedure has been done in the United States involving the PTRCT. This is an investigational research study on the procedure's effectiveness. Currently standard of care at UAB is a stepwise progression. First physical therapy is prescribed anywhere from 2-6 weeks for 1-2 times per week. If physical therapy fails to improve symptoms, then shoulder injections of a combination of steroids and numbing agents are used. If this fails, then surgical procedures are considered. People who enter into the study will be randomly picked (like the flip of a coin) by a computer into 1 of 2 groups: 1) injected with PRP produced from their own blood or 2) combination steroid / anesthetic (current standard of care treatment). This study will enroll 20 participants from the Birmingham area with goal of 10 participants in each group.

2.2 BACKGROUND

Rotator cuff pathology and specifically Partial-Thickness Rotator Cuff Tears (PTRCT) remain a leading cause of shoulder pain in adult patients. Rotator cuff disease is the most common cause of disability related to shoulder pain. Typically tears develop in the supraspinatus tendon and progress gradually because of intrinsic degenerative demands. An association of cuff tears with increasing age has also been demonstrated, with 50% of individuals in their 80s having either symptomatic and/or asymptomatic RCT. There does seem to be a correlation between the presence of pain and progression of tear size indicating that the symptom of pain should warrant close monitoring.

2.3 RISK/BENEFIT ASSESSMENT

2.3.1 KNOWN POTENTIAL RISKS

The most common risks include pain at the injection site, infection at the injection site, no relief of symptoms, worsening of symptoms, deep vein thrombosis, damage to neurovascular structures, bruising, allergic reaction, local toxicity, scar tissue formation, or intravascular infection.

2.3.2 KNOWN POTENTIAL BENEFITS

You may or may not benefit from the procedure. Benefits may include reduction of pain and improved function and strength.

3 STUDY DESIGN

3.1 OVERALL DESIGN

Subjects were randomized into one of two groups (treatment group vs. control group). During the first in-office visit, we obtained an initial assessment and a diagnostic ultrasound with a radiologist. If the subject was in the treatment group, we collected about 10-12 mL of autologous blood from the subject. We used this blood to isolate the PRP and inject it to the treatment area. If the subject was in the control group, an injection combination of steroid and anesthetic (1ml betamethasone + 4.5 ml bupivacaine + 4.5 ml lidocaine) was injected to the treatment area. The subject completed three phone surveys at 3 weeks, 6 weeks, and 6 months. Each subject also completed repeat ultrasound of the shoulder at a visit at 6 months post procedure.

3.2 END OF STUDY DEFINITION

This study was terminated prematurely secondary to lack of successful largely secondary to the COVID pandemic.

4 STUDY POPULATION

4.1 INCLUSION CRITERIA

- Males and females ages 18- 65
- Diagnosed with a partial thickness tear of the supraspinatus tendon via diagnostic MSK ultrasound

4.2 EXCLUSION CRITERIA

- Corticosteroid injections within the past 6 months
- Anti- inflammatory medications 2 weeks prior to the procedure
- Anticoagulation medications 5 days prior to the procedure
- Pregnancy

4.3 SCREEN FAILURES

Subjects enrolled in the study that had a negative diagnostic ultrasounds, showing lack of a tear of the rotator cuff tendon were excluded from the study.

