5.2 MEASURES TO MINIMIZE BIAS: RANDOMIZATION

The study was originally intended for 20 subjects. Subjects number 1 through number 20 were randomized via a randomization calculator prior to starting into the treatment or control groups. As enrollment began, subjects were numbered in the study on a rolling basis and divided into their respective group based on the predetermined randomization.

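### Was a subject's arm already fixed when the eligibility ultrasound was read?

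*Protocol*

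**What the plan says.** Section 4.1 makes the scan part of eligibility: "Diagnosed with a partial thickness tear of the supraspinatus tendon via diagnostic MSK ultrasound". Section 4.3, headed as screen failures, reads: "Subjects enrolled in the study that had a negative diagnostic ultrasounds, showing lack of a tear of the rotator cuff tendon were excluded".

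Section 5.2 describes the allocation list: "Subjects number 1 through number 20 were randomized via a randomization calculator prior to starting into the treatment or control groups". It then describes how the list was used: "As enrollment began, subjects were numbered in the study on a rolling basis and divided into their respective group based on the predetermined randomization". It does not mention the scan.

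Section 3.1 opens its account with randomization and goes on to the first visit, where the scan takes place: "Subjects were randomized into one of two groups (treatment group vs. control group). During the first in-office visit, we obtained an initial assessment".

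Section 2.1 gives the plan: "This study will enroll 20 participants from the Birmingham area with goal of 10 participants in each group".

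Section 5.3 counts 14 patients who enrolled, three excluded for a negative scan, two randomized to control and nine to treatment. Section 8 gives 11 enrolled at termination, split 9 and 2, and reports that no statistical analysis was done. Section 9.1.1.1 requires written consent before any screening procedure.

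**The concern.** If a subject takes a list number on enrollment, and enrollment comes before the scan, the arm is settled while eligibility is still open. Anyone who can see the list could then, knowingly or not, let the arm influence whether a borderline scan counts as a tear. Subjects dropped at that point would also be allocated subjects missing from the reported arms.

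The protocol gives some grounds for this reading. Section 3.1 mentions randomization before the scan, section 5.2 ties numbering to enrollment, and section 4.3 calls subjects with a negative scan enrolled. The two counts attached to 'enrolled' (14 and 11) make it harder to rule out. At stake is whether 9 and 2 are everyone to whom an arm was assigned, and whether the comparison was open to selection after allocation.

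**Working it through.** **1. Do the counts agree?** Inputs from section 5.3: 14 enrolled, 3 negative scans, 9 treatment, 2 control. Input from section 8: 11 enrolled.

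- 14 − 3 = 11
- 9 + 2 = 11

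The section 8 total is reproduced. The two sections use one word for two stages; they do not contradict each other in number.

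**2. Which order does each section support?**

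| Section | What it contributes | Points to |
|---|---|---|
| 5.3 | Removes 3 on the scan, then describes only the other 11 as randomized | number after scan |
| 4.3, heading | Negative scans classed as screen failures | number after scan |
| 9.1.1.1 | Consent precedes screening, so a screen failure can loosely be called enrolled | compatible with after |
| 3.1 | Mentions randomization before the visit, in an overview | weakly, before |
| 5.2 | Numbers given on a rolling basis; scan not mentioned | neither alone |
| 4.3, text | Negative scans called enrolled; no number or arm mentioned | neither alone |

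Number-before-scan follows from 4.3 and 5.2 only if 'enrolled' in 4.3 means that a list number had been taken. That is the point in question.

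**3. What would the other order imply?** If all 14 held numbers and t of the three excluded were in the treatment arm, the split would be (9 + t) : (5 − t):

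- t = 0: 9:5
- t = 1: 10:4
- t = 2: 11:3
- t = 3: 12:2

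If the list held exactly 10 per arm (an assumption, since section 2.1 gives that only as a goal), then 9 + t ≤ 10. Only 9:5 and 10:4 would be possible. Neither can be confirmed or excluded from the document.

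**4. Does the 9:2 split help?** It depends on how the list was built, which is not stated.

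- List of exactly 10 per arm, 11 numbers used: P(2 or fewer controls) = (450 + 10)/167960 = 0.0027. In either direction, 920/167960 = 0.0055.
- Independent coin flips: (1 + 11 + 55)/2048 = 67/2048 = 0.033. In either direction, 134/2048 = 0.065.

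Section 2.1 calls 10 per group a goal and likens allocation to a coin flip ("People who enter into the study will be randomly picked (like the flip of a coin) by a computer into 1 of 2 groups"), so the smaller figure rests on a forced balance that the text does not state. Neither figure bears on the question: if exclusion was unrelated to arm, the 11 who remain have the same distribution whether numbers attached before or after the scan. The split therefore cannot tell the two orders apart.

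**The case for a change.** The best case for a change is that the order of eligibility and allocation is a design matter, not something to leave to an analysis plan. The protocol addresses it under a heading about minimizing bias and leaves it open. The benign reading also has a cost: if 'enrolled' means consented, section 5.2 taken literally numbers people before the scan, so numbering after the scan requires the word to change meaning between 4.3 and 5.2. The replacement rule in section 6.2, for subjects randomized but not treated, does not say whether negative scans come under it. A look at the enrollment log would settle the matter cheaply.

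Much of this stands. The order is not stated, the wording is loose, and a reader cannot prove from the text that the three excluded subjects held no numbers. Anyone writing up the trial would do well to report 14 consented, 3 screen failures and 11 randomized. But the word does shift meaning elsewhere in this protocol (14 in 5.3, 11 in 8), so a shift between 4.3 and 5.2 is no strain. Silence about concealment is missing detail, not an error. Nothing in the document shows that an arm was known when a scan was read.

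**Conclusion.** No change follows. The 14 and 11 are the same cohort before and after three exclusions, so the difference is a slip of terminology. On timing, the section that counts randomized subjects and the heading of 4.3 favour the harmless order. The contrary order is an inference that the text permits but does not make.

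The most that could be affected is the reported arm of three subjects out of 14. Recruitment is over, so rewording cannot alter how numbers were given out. No statistical analysis was done, so no treatment estimate, interval or conclusion could move. This rests on taking sections 5.3 and 8 at face value. If the enrollment log showed that the three excluded subjects held list numbers, the subject flow should say so, but there would still be no result to correct.

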4.4 STRATEGIES FOR RECRUITMENT AND RETENTION

Subjects were recruited from an outpatient Physical Medicine and Rehabilitation clinic at the University of Alabama. Each subject was given information regarding the study requirements and follow up obligations prior to enrollment and signed to complete based on their confidentiality agreement form.

5 STUDY INTERVENTION

5.1 STUDY INTERVENTION(S) ADMINISTRATION

5.1.1 STUDY INTERVENTION DESCRIPTION

Experimental Group

Withdraw 10-12 mL of blood from your arm.
Process blood to isolate the PRP.
Skin will be cleaned to sterilize the surface.
Ultrasound machine with sterile gel will be used to visualize injection target.
Inject the PRP into the targeted area for the actual treatment.

Control Group

Skin will be cleaned to sterilize the surface.
Ultrasound machine with sterile gel will be used to visualize injection target.
Inject combination (steroid and anesthetic) 1ml betamethasone + 4.5ml bupivacaine + 4.5ml lidocaine.

5.2 MEASURES TO MINIMIZE BIAS: RANDOMIZATION

The study was originally intended for 20 subjects. Subjects number 1 through number 20 were randomized via a randomization calculator prior to starting into the treatment or control groups. As enrollment began, subjects were numbered in the study on a rolling basis and divided into their respective group based on the predetermined randomization.

5.3 STUDY INTERVENTION COMPLIANCE

Overall, there was poor compliance in this study. We had 14 patients enroll originally. Three patients had a negative diagnostic ultrasound thus were excluded from the study. Two patients were randomized into the Control Group, and both completed all study requirements. Nine patients were randomized into the Treatment group; of these 9 patients, 4 did not complete all follow up questioners and 2 did not complete the 6 month follow up ultrasound.

5.4 CONCOMITANT THERAPY

Subjects were asked to avoid use of NSAIDs, including Advil, Aleve, Ibuprofen, Naproxen, Voltaren, Aspirin, for six weeks after the injection, as it will interfere with the beneficial effects of the PRP treatment. Tylenol (acetaminophen), ice and heat were allowed as needed for pain relief.
Activity: Normal day to day activity was permitted. Subjects were asked to refrain from any significant activity involving the injected site for first 3 days after procedure. Gradually increase activity over the next 6-12 weeks as tolerated.

6 STUDY INTERVENTION DISCONTINUATION AND SUBJECT DISCONTINUATION/WITHDRAWAL

6.1 DISCONTINUATION OF STUDY INTERVENTION

Study intervention was a one- time injection. No discontinuation was required in the study.

6.2 SUBJECT DISCONTINUATION/WITHDRAWAL FROM THE STUDY

Subjects are free to withdraw from participation in the study at any time upon request.

An investigator may discontinue or withdraw a subject from the study for the following reasons:

- Significant study intervention non-compliance
- If any clinical adverse event (AE), laboratory abnormality, or other medical condition or situation occurs such that continued participation in the study would not be in the best interest of the subject

Subjects who sign the informed consent form and are randomized but do not receive the study intervention may be replaced. Subjects who sign the informed consent form, and are randomized and receive the study intervention, and subsequently withdraw, or are withdrawn or discontinued from the study, will not be replaced.

6.3 LOST TO FOLLOW-UP

A subject will be considered lost to follow-up if he or she fails to return for 2 scheduled visits and is unable to be contacted by the study site staff.

The following actions must be taken if a subject fails to be available for a required study visit:

- The site will attempt to contact the subject and reschedule the missed visit and counsel the subject on the importance of maintaining the assigned visit schedule and ascertain if the subject wishes to and/or should continue in the study.
- Before a subject is deemed lost to follow-up, the investigator or designee will make every effort to regain contact with the subject (where possible, 3 telephone calls and, if necessary, a certified letter to the subject's last known mailing address or local equivalent methods). These contact attempts should be documented in the subject's medical record or study file.
- Should the subject continue to be unreachable, he or she will be considered to have withdrawn from the study with a primary reason of lost to follow-up.

7 STUDY ASSESSMENTS AND PROCEDURES

7.1 STUDY ASSESSMENTS

Subjects were required to complete 3 telephone interviews to repeat questionnaire (SPADI) at week 3, week 6 and 6 months.

At 6 months after initial procedure subjects were schedule for repeat diagnostic MSK ultrasound which was the end of the study.

7.2 ADVERSE EVENTS AND SERIOUS ADVERSE EVENTS

7.2.1 DEFINITION OF ADVERSE EVENTS (AE)

Adverse event means any untoward medical occurrence associated with the use of an intervention in humans, whether or not considered intervention-related (21 CFR 312.32 (a)).

7.2.2 DEFINITION OF SERIOUS ADVERSE EVENTS (SAE)

An adverse event (AE) is considered “serious” if, in the view of either the investigator or sponsor, it results in any of the following outcomes:

- Death
- A life-threatening adverse event (of note, the term “life-threatening” refers to an event in which the subject was at risk of death at the time of the event, rather than to an event which hypothetically might have caused death if it were more severe)
- inpatient hospitalization or prolongation of existing hospitalization
- a persistent or significant incapacity or substantial disruption of the ability to conduct normal life functions
- or a congenital anomaly/birth defect.

Important medical events that may not result in death, be life-threatening, or require hospitalization may be considered serious when, based upon appropriate medical judgment, they may jeopardize the subject and may require medical or surgical intervention to prevent one of the outcomes listed in this definition. Examples of such medical events include allergic bronchospasm requiring intensive treatment in an emergency room or at home, blood dyscrasias or convulsions that do not result in inpatient hospitalization, or the development of drug dependency or drug abuse.

7.2.3 CLASSIFICATION OF AN ADVERSE EVENT

7.2.3.1 SEVERITY OF EVENT

For adverse events (AEs), the following guidelines will be used to describe severity:

- **Mild** – Events require minimal or no treatment and do not interfere with the subject’s daily activities.
- **Moderate** – Events result in a low level of inconvenience or concern with the therapeutic measures. Moderate events may cause some interference with functioning.
- **Severe** – Events interrupt a subject’s usual daily activity and may require systemic drug therapy or other treatment. Severe events are usually potentially life-threatening or incapacitating. Of note, the term “severe” does not necessarily equate to “serious.”

7.2.3.2 RELATIONSHIP TO STUDY INTERVENTION

All adverse events (AEs) must have their relationship to study intervention assessed by the clinician who examines and evaluates the subject based on temporal relationship and his/her clinical judgment. The degree of certainty about causality will be graded using the categories below. In a clinical trial, the study product must always be suspect.

- **Related** – The AE is known to occur with the study intervention, there is a reasonable possibility that the study intervention caused the AE, or there is a temporal relationship between the study intervention and event. Reasonable possibility means that there is evidence to suggest a causal relationship between the study intervention and the AE.

- **Not Related** – There is not a reasonable possibility that the administration of the study intervention caused the event, there is no temporal relationship between the study intervention and event onset, or an alternate etiology has been established.

7.2.3.3 EXPECTEDNESS

The Principal Investigator will be responsible for determining whether an adverse event (AE) is expected or unexpected. An AE will be considered unexpected if the nature, severity, or frequency of the event is not consistent with the risk information previously described for the study intervention.

7.2.4 TIME PERIOD AND FREQUENCY FOR EVENT ASSESSMENT AND FOLLOW-UP

The occurrence of an adverse event (AE) or serious adverse event (SAE) may come to the attention of study personnel during study visits and interviews of a study subject presenting for medical care, or upon review by a study monitor.

All AEs including local and systemic reactions not meeting the criteria for SAEs will be captured on the appropriate case report form (CRF). Information to be collected includes event description, time of onset, clinician's assessment of severity, relationship to study product (assessed only by those with the training and authority to make a diagnosis), and time of resolution/stabilization of the event. All AEs occurring while on study must be documented appropriately regardless of relationship. All AEs will be followed to adequate resolution.

Any medical condition that is present at the time that the subject is screened will be considered as baseline and not reported as an AE. However, if the study subject's condition deteriorates at any time during the study, it will be recorded as an AE.

Changes in the severity of an AE will be documented to allow an assessment of the duration of the event at each level of severity to be performed. AEs characterized as intermittent require documentation of onset and duration of each episode.

The Study Coordinator will record all reportable events with start dates occurring any time after informed consent is obtained until 7 (for non-serious AEs) or 30 days (for SAEs) after the last day of study participation. At each study visit, the Study Coordinator will inquire about the occurrence of AE/SAEs since the last visit. Events will be followed for outcome information until resolution or stabilization.

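### Recording of new adverse events stops 7 or 30 days after participation ends, although exposure is a single injection, so anyone who leaves early has a shorter safety window

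*Protocol*

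**What the plan says.** - **Recording window.** Protocol section 7.2.4 starts recording at consent and continues "until 7 (for non-serious AEs) or 30 days (for SAEs) after the last day of study participation". It gives no end date counted from the injection. The same section says "At each study visit, the Study Coordinator will inquire about the occurrence of AE/SAEs since the last visit".
- **Exposure and follow-up.** Section 6.1: "Study intervention was a one- time injection". The synopsis gives a six-month observation period. Section 7.1: "Subjects were required to complete 3 telephone interviews to repeat questionnaire (SPADI) at week 3, week 6 and 6 months", and at 6 months a "repeat diagnostic MSK ultrasound which was the end of the study".
- **Leaving the study.** Section 6.2: "Subjects are free to withdraw from participation in the study at any time upon request". It also allows the investigator to withdraw a subject for marked non-compliance, or because of an adverse event or other condition that makes staying in the study undesirable. Under section 6.3, after repeated contact attempts, an unreachable subject is handled thus: "he or she will be considered to have withdrawn from the study with a primary reason of lost to follow-up". Neither section provides for safety contact afterwards, and section 6.3 does not say which day counts as such a subject's last day.
- **What happened.** Section 5.3: "Two patients were randomized into the Control Group, and both completed all study requirements". Of the nine PRP subjects, four did not complete all questionnaires and two missed the 6-month ultrasound. Section 8 reports 5 of 11 subjects with incomplete data, describes them as lost to follow-up at some point, and states that no statistical analysis was done.

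**The concern.** After a single injection, the period in which a late event could be attributed to treatment runs from the injection and is the same for everyone. A window tied to participation makes its length depend on when and why a subject leaves. The provision to follow events until they resolve or stabilize does not close the gap, because it concerns events already recorded, not new ones.

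Investigator withdrawal shows the weakness most clearly. A subject withdrawn because of an adverse event may be fully reachable, yet new events in that subject stop being recorded 7 or 30 days later. Applied as written, the rule can therefore shorten observation selectively, in subjects who have already had an event. A simple proportion of subjects with an event would then compare people watched for different lengths of time, with nothing in the count to show it.

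**Working it through.** **Inputs.** Window extensions of 7 and 30 days (section 7.2.4); contacts at week 3, week 6 and 6 months (section 7.1); arm sizes and missed assessments (section 5.3); 5 of 11 incomplete (section 8). Assumption: 6 months = 182 days, counted from the injection.

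**Step 1. Reproduce the protocol's counts.** 14 enrolled − 3 with a negative ultrasound = 11 = 9 PRP + 2 control. The number of PRP subjects missing something is 4 + 2 − overlap, so it lies between 4 (overlap 2) and 6 (overlap 0). The stated 5 fits with overlap 4 + 2 − 5 = 1. Both controls were complete, so all five are PRP subjects.

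**Step 2. Window length.** Window = last day of participation + 7 (non-serious) or + 30 (serious).

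| Participation ends | Non-serious AEs | Share of completer's | SAEs | Share of completer's |
|---|---|---|---|---|
| Injection day (0) | 7 days | 7/189 = 4% | 30 days | 30/212 = 14% |
| Week 3 (day 21) | 28 days | 28/189 = 15% | 51 days | 51/212 = 24% |
| Week 6 (day 42) | 49 days | 49/189 = 26% | 72 days | 72/212 = 34% |
| 6 months (day 182) | 189 days | 100% | 212 days | 100% |

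The first three rows are illustrations. The protocol does not say that anyone left on those days.

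**Step 3. Who could have had a shortened window here.** With an overlap of 1, the five incomplete PRP subjects divide as follows:
- 4 − 1 = 3 missed questionnaires only. They attended the 6-month ultrasound, which section 7.1 treats as the end of the study, so their window is full.
- 2 − 1 = 1 missed the ultrasound only. This subject completed every questionnaire, including the 6-month call, so took part to 6 months.
- 1 missed both. If the missed questionnaire was the 6-month one, the window may have been shortened. If it was only an earlier one, it was not.

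Result: 0 or 1 of 9 PRP subjects, and 0 of 2 controls.

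**Step 4. Check against section 8.** If all five had left before 6 months, five would have missed the ultrasound. Section 5.3 says two did. The two sections agree on the count but not on the description.

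**Step 5. The arm imbalance in incomplete data.** 5/9 against 0/2. Given 5 incomplete among 11, the chance that both controls are complete is C(6,2)/C(11,2) = 15/55 = 0.27. The two-sided Fisher p-value is (15 + 10)/55 = 0.45.

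**The case against.** The strongest case for leaving the text alone is that the rule is coherent and contradicts nothing else in the protocol. A completer is covered for all six months and beyond. Early loss is mainly a problem of lost contact, and section 6.3 already asks for repeated telephone calls and, if needed, a certified letter. Rewording the window cannot recover someone who stays unreachable. No between-arm comparison of adverse events is specified in the protocol, and no analysis was done.

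Much of this stands. The rule is a design choice, not an error, and changing it helps only subjects who stop assessments but can still be contacted or whose records can be reviewed. That group is not empty in principle, because section 6.2 allows the investigator to withdraw a reachable subject.

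A reader might also infer more than the protocol supports:
- *That five of nine PRP subjects lost safety observation against none of the controls.* A missed questionnaire does not end participation, and step 3 reduces five to at most one.
- *That subjects doing badly leave first, so the rule flatters PRP.* The protocol does not give individual reasons for the losses, so this is conjecture.
- *That PRP caused the incomplete follow-up.* With 9 against 2 subjects, the split is compatible with chance.

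One uncertainty runs the other way. Section 7.2.4 ties the inquiry about events to visits, and the only post-injection visit described is at 6 months. If the telephone interviews do not count as visits, a subject who misses the 6-month visit has no scheduled inquiry after the injection.

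**Conclusion.** The point holds as a limitation of the rule in section 7.2.4. For a one-time injection with six months of observation, tying the end of recording to participation could cut the non-serious window to about 15% of a completer's for a week-3 leaver, and to about 26% for a week-6 leaver. The corresponding SAE shares are about 24% and 34%.

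In this trial its reach is at most 1 of 9 PRP subjects, possibly none, and no controls. That is not evidence of differential loss of safety data between the arms.

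The conclusion rests on four assumptions: the last day of participation means each subject's own last day, which is the natural reading but is not spelled out; six months is 182 days; the five incomplete subjects in section 8 are the same people as in section 5.3; and attending the 6-month ultrasound or completing the 6-month call counts as taking part to 6 months. This is a low-cost improvement, not a serious defect.

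**What to change.** 1. **Section 7.2.4.** Count the window from the injection. Suggested wording: *For every injected subject, new adverse events are recorded from consent to 6 months plus 7 days after the injection, and serious adverse events to 6 months plus 30 days. This includes subjects who stop study assessments or are withdrawn by the investigator, provided they still permit contact or record review.*
2. **Sections 6.2 and 6.3.** Refer to that window, and define the last day of participation for a subject who is lost, in the same way for both arms.
3. **Reporting of this trial.** Give the actual safety observation time per arm beside any adverse event counts.
4. **Sections 5.3 and 8.** Reconcile the description of the five incomplete subjects: state how many missed a questionnaire only, the ultrasound only, or both, and when each was last in contact.

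**Cost.** Wording in the protocol and consent form, and one call or chart review per early leaver. Subjects who refuse contact and record review, or who cannot be reached, remain unobserved. Because the trial has ended, items 1 and 2 serve any reuse of this protocol; items 3 and 4 can be done now.
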